**Participant Incentives:**

In order to encourage participation and acknowledge the time involved in questionnaire completion, we are providing \$10 to each participant. These incentives are provided in advance of the completion of the questionnaires as it has been shown that it is at this time point, rather than after completion of questionnaires, that they are most effective. Interview subjects will receive \$25 after the interview as an acknowledgement of their contribution to the study. 'Thank you' payments are kept small to minimize coercion or undue influence.

## 6 STUDY INTERVENTION(S) OR EXPERIMENTAL MANIPULATION(S)

### 6.1 STUDY INTERVENTION(S) OR EXPERIMENTAL MANIPULATION(S) ADMINISTRATION

### 6.1.1 STUDY INTERVENTION OR EXPERIMENTAL MANIPULATION DESCRIPTION

This study is a randomized trial of an intervention to improve outcomes for patients and their family by supporting, modeling, and teaching communication strategies that enable patients and their families to secure care in line with a patient's goals over an illness trajectory, beginning in the ICU and continuing to care in the community.

If patients with decisional capacity and family agree to participate, they will complete informed consent procedures and HIPAA authorization. If patients do not have decisional capacity but are eligible for the study, LNOK will complete informed consent procedures and HIPAA authorization. Subjects assigned to the intervention arm will work with a communication facilitator and will complete assessments/measures; subjects assigned to the control arm will complete assessments/measures only. Family will be clustered under patients.

A short study summary will be included in the patient's electronic health record (EHR). This summary will be included for both the intervention and control patients.

- Control Arm/Usual Care: Patients and family members randomized to the control arm will complete the same study measures at all data collection points, but the facilitator will not be involved. Instead, these subjects will be contacted prior to the follow-up questionnaires at 1-month, 3-months and 6-months from randomization. During the calls for these subjects, they will be asked if they have any questions about study procedures and be reminded about upcoming surveys. The revised "Information & Resources Provision Arm/Comparator" study arm is an adaptation to the Facilitator Protocol for use during the COVID-19 pandemic. For those randomized to "Control/Usual Care," participation in this comparator arm will be available at the participant's request. The goal of this comparison group is to offer family members a contact person for questions related to their loved one's care. The resource person (trained study staff or research RN) will contact family members within 1-2 days of enrollment and randomization. They will introduce themselves as a resource for finding or providing information in this stressful and difficult time. All contact will be by telephone or UW HIPAA-compliant Zoom on the following schedule:
  - a. Within 1-2 days of randomization
  - b. Within 1-2 days of transfer to acute care.
  - c. Within 1-2 days of hospital discharge.

The resource person is intended to provide information and help families connect with the right person at the hospital or on the patient's healthcare team to provide help and support.

- Intervention Administration: Intervention activities will be conducted with intervention subjects only. Beginning during the ICU stay, and continuing for three months, facilitators will interact in person, by telephone, or UW HIPAA-compliant Zoom with patients and family subjects, and those clinicians (physicians, nurses, social workers, spiritual care, etc.) involved with patients' care.

After baseline data collection, the facilitator will begin providing the intervention to patients in the ICU and their families. The intervention will include communication activities such as: discussion of values, provision of educational and informational materials as needed, and support and mediation if conflicts arise among the family or between family and the clinical team. The facilitators will provide these activities in a manner consistent with the subjects' preferred attachment styles that are assessed at baseline.

During the patient's hospitalization, the facilitators may enter notes in the electronic health record (EHR) to relay information in the patient's chart that is relevant to communication between patient/family and the clinical team, for example: "The patient's daughter expressed questions about rehab;" or "The patient's son may be reluctant to ask questions, informing him about what to expect next may be helpful." The facilitators also enter a Research Intervention Introductory note into the patient EHR so inform the clinical staff about their role with the patient/family. These notes will appear under "Chart Review/Notes/Type: Research Note" in the EHR system. Additionally, we will have signage in the hospital room noting that study facilitators are available for the patient enrolled in the intervention. The sign will mirror the note in the EHR.

After the ICU stay, the facilitator will guide the patient and family through transitions to the acute care floor, discharge to home/rehabilitation or skilled nursing facility (SNF). Outside the hospital in the community, the facilitator will be available to make visits to a SNF or rehabilitation unit and/or the patient's home and participate in outpatient clinic visits. The primary mission of the facilitator at these transitional contacts will be to support, model, and teach the communication skills that advance self-efficacy, outcome expectations, and behavioral capacity for goals-of-care discussions that will advance care in line with those goals and across transitions.

#### 6.1.2 ADMINISTRATION AND/OR DOSING

During the ICU stay, facilitators will interact in person with patients, family, and many types of clinicians (physicians, nurses, social workers, etc.). Following the ICU stay, facilitators will interact with patients, family and clinicians in person and by phone for 3 months from randomization (when most first readmissions occur) or for 1 month after a patient death occurring in the first 3 months. In-person contacts may include visits to patients' homes and/or care facilities; phone contacts will include calls to patients, families and clinicians. Because prior studies suggest frequent contact is important, the schedule for contact will be a minimum of every 48 hours in the hospital, within 72 hours of change in care setting, weekly for a month after hospital discharge, and then twice monthly for the 3 months. The facilitators will use clinical judgment if they feel more frequent contact is warranted, and patients and families will have access to facilitators through phone and email 5 days per week. Facilitators will be available to attend clinic visits with patients. In addition to checking directly with patients/families during regular contacts (calls, visits), facilitators will also access the EHR to ensure they have accurate information about appointments and treatment plans and will document their interactions and key points for the clinical team.

We strive to have the same facilitator work with the patient and family throughout the study. Facilitators will encourage referral to inpatient or outpatient palliative care services when palliative care needs (i.e., communication, decision-making, and symptom needs) are identified. Based on prior studies, sample size, and time projections, we estimate facilitators can have a caseload of 20 patients/facilitator/month, accounting for 1.6 FTE. This estimate is based on the following: 1) 4-5 new patients/month per facilitator; 2) an average of 12-15 visits/patient (i.e., 4-5 during the ICU stay, 4-5 during the first month following the ICU, and 4-5 during the remaining study period; 3) an average of 20-30 minutes per visit; and 4) 1 hour of preparation per visit. We will attempt to document facilitator contacts for each patient and family to assess intervention fidelity, "dose," and costs.

#### 6.2 FIDELITY

### 6.2.1 INTERVENTIONIST TRAINING AND TRACKING

- Training of facilitators: Training will be provided by all investigators and consultants with specific roles in: facilitator communication skills, decision support, the use of attachment theory, and mediation. Training will address the use of these skills across care settings (e.g., inpatient, outpatient, home, care facility). Communication training will include identification of goals of care, incorporating principles of advance care planning and the facilitated values history. Training in the decision support will address the use of goals to support decision-making. Attachment theory training will include understanding the four attachment styles, the consequences of these styles for communication, and the approaches most appropriate for each style. Mediation training will cover skills associated with assessment and preparation; mediator opening; presentation of the case, information gathering and exchange; development and evaluation of options; and resolution. Facilitators will participate in role-playing exercises during a two-day training and they will be required to demonstrate mastery of intervention skills before starting and during fidelity checks. We have conducted similar training previously with good results. We will expand the training manual to enhance dissemination of the intervention to other institutions.
- Intervention fidelity: To ensure scientific rigor, intervention fidelity will be assessed with methods outlined by the NIH Behavioral Treatment Fidelity Workgroup on consistency in dose, providers, delivery, receipt, and enactment of interventions. Facilitators will meet weekly with investigators to discuss the intervention subjects and ensure intervention fidelity overall and between facilitators. We will use an intervention checklist assessing completion of all components. If concerns arise regarding fidelity, the appropriate expert will be consulted. There will also be a formal fidelity check via audio-recording and review of 10% of encounters. Refresher-training sessions will be conducted regularly.

### 6.3 MEASURES TO MINIMIZE BIAS: RANDOMIZATION AND BLINDING

The unit of randomization is the patient. The potential for contamination is minimized because the focus of the intervention is specific to the individual patient and family and tailored to their needs. Randomization will occur in variable-sized blocks stratified by site. Family will be clustered under patients.

The intervention precludes blinding clinicians, patients, or family to treatment group. However, we will blind study staff involved in data collection to group assignment via surveys send and completed by mail and online. A number of the outcomes could theoretically allow the introduction of bias if patients or family in the intervention arm give different ratings for reasons other than the intervention (i.e., to please researchers). Therefore, we will not highlight the primary outcome during the consent process, and all participants will receive contact with study staff for completion of study materials which will help mitigate this potential source of bias.

### 6.4 STUDY INTERVENTION/EXPERIMENTAL MANIPULATION ADHERENCE

N/A

### 6.5 CONCOMITANT THERAPY

N/A

#### 6.5.1 RESCUE THERAPY

N/A

### 7 STUDY INTERVENTION/EXPERIMENTAL MANIPULATION DISCONTINUATION AND PARTICIPANT DISCONTINUATION/WITHDRAWAL

#### 7.1 DISCONTINUATION OF STUDY INTERVENTION/EXPERIMENTAL MANIPULATION

Subjects may be withdrawn from the study without their consent if they can no longer meet the study requirements (e.g. no longer able to complete questionnaires). For any withdrawal, investigator or subject initiated, we will retain all data that was previously collected and continue to collect chart abstraction data, unless the subject specifically requests that the data no longer be used and access to records is revoked.

#### 7.2 PARTICIPANT DISCONTINUATION/WITHDRAWAL FROM THE STUDY

Participation is voluntary and participants may withdraw from the study at any time for any reason.

An investigator may discontinue a participant from the study for the following reasons:

- The participant meets an exclusion criterion (either newly developed or not previously recognized) that precludes further study participation,
- Lost-to-follow up; unable to contact subject,
- Any event or medical condition or situation occurs such that continued collection of follow-up study data would not be possible.

The reason for participant discontinuation or withdrawal from the study will be recorded study tracking database. Subjects who sign the informed consent form and are randomized but do not receive the study intervention will be replaced in order to meet enrollment goals. Subjects who sign the informed consent form, and are randomized and receive the study intervention, and subsequently withdraw, or are discontinued from the study, will be replaced in order to meet enrollment goals.

#### 7.3 LOST TO FOLLOW-UP

A participant will be considered lost to follow-up if he or she fails to return any of the study questionnaires scheduled visits and study staff are unable to contact the participant after at least 3 attempts at each time point.

The following actions must be taken if a participant fails to return a study questionnaire:

- The RC will attempt to contact the participant, resend the survey packet or online link, and offer to complete the study instruments by phone. The RC will remind the participant that we value their responses and participation.

- Should the participant continue to be unreachable, he or she will be considered to have withdrawn from the study with a primary reason of lost to follow-up.

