## 9.2 SAMPLE SIZE DETERMINATION

The primary focus for sample size estimation is the primary outcome: mean family member depression over 6 months as assessed by the HADS depression subscale. For all calculations, we assume a two-sided test with a significance level of 0.05. If we assume 300 total family members (1 family member per patient and 150 per arm), a standard deviation of HADS depression scores of 4.2 points in both arms, 3 measurements of depression (at 1,3, and 6 months), and an intraclass correlation (ICC) of 0.2, we will be able to detect a difference in mean depression of at least 0.93 points with 80% power and 1.07 points with 90% power (Power Table Below). These detectable differences at 80% power become 0.86 if the ICC is 0.1 and 1.05 if the ICC is as high as 0.4. If we had only 1 measurement instead of 3 per family member or, equivalently, if the ICC were 1, we would have 80% power to detect a difference of at least 1.36 points. Across all of these varying conditions, detectable differences are slightly within or below estimates of the minimally clinically important difference (MCID) of 1.6 to 2.0 available from the literature, suggesting we will have adequate power to identify a minimally clinically important difference. Although these MCIDs and minimum detectable effects are just estimates, they provide the best available evidence that power will be adequate to detect relatively small but important differences. We anticipate >80% complete data for all outcomes so we will randomize 376 patients to achieve 300 patients and at least 300 family members with complete data. If our response rate is 70%, then we would expect responses for 263 patients and at least 263 family members and with an ICC of 0.2, we would be able to detect a difference in mean depression of at least 0.99 points with 80% power. If we have more than 1 family member per patient (1.5 is expected), we will be able to detect smaller differences at the same power. In addition, we have 80-90% power to detect reasonable effects for other continuous outcomes in Aim 1. For the binary outcome of goal-concordance care, we have about 80% power to detect a difference in proportion concordant of 0.6 and 0.7, with 3 measurements from each of 300 total participants and an ICC of 0.13; the estimate of 0.6 for the controls is from a prior study and our preliminary data. We targeted power to identify differences within or slightly less than available estimates of “minimally important clinical differences” so that we would be confident that we would be powered to detect a minimally important clinical difference.

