### 9.4.2 ANALYSIS OF THE PRIMARY ENDPOINT(S)

- Specific Aim 1, Primary Endpoint

Our primary outcome is family member symptoms of depression over the 6-months post-randomization period. We will follow the intention-to-treat principle. Our primary analysis will use a linear mixed effects model with family member symptoms at all time points (1,3,6 months) as the response, main effects for intervention and time points, and a random effect to account for multiple measurements (time points) per family member. Given multiple family members per patient, we will also include a random effect for family. Time point is included as a factor variable to allow for nonlinear effects. We will also adjust for site, since randomization is stratified by site, and consider adjustment for response (symptoms of depression for primary outcome) at baseline (randomization). This model allows the average response to be different at 1, 3, and 6 months, but assumes the intervention has the same effect at each of these times. The secondary analysis allows the effect of intervention to be different across time by including an interaction between time and intervention. The advantage of using the data at all three time points and

a mixed model approach is that we can gain precision; it also allows for missing responses, assuming the responses are missing at random. We will use a similar approach for the other continuous family and patient outcomes, and a generalized linear mixed effects model for the binary outcome of goal-concordant care. As a sensitivity analysis, we will consider models including only one family member per patient, chosen randomly.

---

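### Section 7.3 can be read as withdrawing a relative who cannot be reached at a single wave, which would forgo later HADS-D scores that the primary model could use

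*Combined protocol and SAP*

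**What the plan says.** Section 7.3 has two parts that do not clearly agree.

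- **Definition.** A participant is lost to follow-up when two conditions hold together: questionnaires are not returned, and staff cannot make contact after at least three tries at each time point. This can mean one wave or all of them.
- **Action list.** It opens: "The following actions must be taken if a participant fails to return a study questionnaire". The trigger is a single form. Staff then try to make contact, resend the packet or link and offer completion by phone. If that fails: "Should the participant continue to be unreachable, he or she will be considered to have withdrawn from the study".

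The related sections are these.

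- **7.2** lists "Lost-to-follow up; unable to contact subject" among the reasons for which an investigator may discontinue someone, and says that withdrawn or discontinued subjects are replaced.
- **7.1** keeps data already collected and continues chart abstraction after withdrawal. It does not mention further questionnaires.
- **4.1** and **8.1** (and **5.5** for the intervention arm) set out contact at 1, 3 and 6 months, with no condition on an earlier response.
- **9.4.2** takes symptoms at 1, 3 and 6 months as the response in the primary mixed model and says of that model: "it also allows for missing responses, assuming the responses are missing at random".

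**The concern.** The primary model can use a relative who misses one wave and answers another. A follow-up rule that stops at the first missed wave would discard that advantage, because an intermittent gap becomes dropout.

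The effect is greatest at month 1. Baseline HADS-D is at most a covariate in 9.4.2, so a relative withdrawn at month 1 supplies no response at all, although 9.3 puts every randomized family member in the analysis population. The IES-6, collected only at follow-up, is lost as well. The multiple imputation in 9.4.1 draws on outcomes from previous time points, and for this relative those are baseline values only. Replacement under 7.2 may restore the headcount but not the missing outcomes.

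There is also a conduct problem. Two coordinators following the same protocol could treat the same relative differently, one closing the record and the other sending the 3-month form.

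**Working it through.** **Step 1: the plan's own figure.** Inputs from 9.2: "For all calculations, we assume a two-sided test with a significance level of 0.05"; 150 relatives per arm, one per patient; "a standard deviation of HADS depression scores of 4.2 points in both arms"; m = 3 follow-up measurements; ICC 0.2.

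MDD = (z₀.₉₇₅ + z_power) × SD × √[(1 + (m − 1) × ICC)/m] × √(2/n per arm)

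= (1.960 + 0.842) × 4.2 × √(1.4/3) × √(2/150) = 0.928, against the stated 0.93.

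The other stated figures also reproduce: 1.074 (1.07 at 90% power), 0.859 (0.86 at ICC 0.1), 1.052 (1.05 at ICC 0.4), 1.359 (1.36 with one measurement) and 0.991 (0.99 with 263 relatives). For attrition, 300/0.8 = 375, consistent with 376 randomized.

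**Step 2: cost of stopping at the first missed wave.** The documents give no wave-specific non-response, so this is an assumption: 376 relatives (one per patient), and an independent chance q at each wave of being both unreturned and unreachable. A relative with m scores contributes information m/(1 + (m − 1) × ICC). At ICC 0.2 that is 1, 1.667 and 2.143 for m = 1, 2 and 3. With average information I per relative, MDD = (z₀.₉₇₅ + z₀.₈₀) × 4.2 × √[4/(376 × I)].

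Worked for q = 20%:

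- Every wave attempted: 51.2% give three scores, 38.4% two, 9.6% one. I = 0.512 × 2.143 + 0.384 × 1.667 + 0.096 × 1 = 1.833, so MDD = 0.896.
- Withdrawn at first miss: 51.2% give three, 12.8% two, 16% one, 20% none. I = 0.512 × 2.143 + 0.128 × 1.667 + 0.16 × 1 = 1.470, so MDD = 1.001.

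| q per wave | MDD, all waves attempted | MDD, withdrawn at first miss | HADS-D scores | Month-6 response |
|---|---|---|---|---|
| 10% | 0.859 | 0.908 | 1015 vs 917 | 90% vs 73% |
| 20% | 0.896 | 1.001 | 902 vs 734 | 80% vs 51% |
| 30% | 0.942 | 1.113 | 790 vs 576 | 70% vs 34% |

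The share with all three scores, (1 − q)³, is the same in both columns. The rule costs only the scores of partial responders: 98, 168 and 214 for the three rows.

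Over ICC 0.1 to 0.4 the increase in MDD runs from 0.846 − 0.802 = 0.04 (ICC 0.1, q = 10%) to 1.219 − 1.029 = 0.19 (ICC 0.4, q = 30%).

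**Step 3: dependence on who comes back.** Suppose instead that 20% miss month 1 only, and a share r of them would answer at both later waves if approached. Scores lost are 376 × 0.20 × r × 2: none for r = 0, 75 for r = 0.5 and 150 for r = 1. The MDD is 0.927 with withdrawal, against 0.927, 0.885 and 0.848 without it. If those missed at month 1 would never answer, the rule costs nothing. A miss at month 6 costs no later score in any case.

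**The case against.** The strongest reply is that 7.3, read as a whole, does not say this. Withdrawal needs failed re-contact as well as a missing form, and the closing line assigns the status that the opening sentence defines, so the two are naturally read together. The contact schedule does not stop after a miss. Month-1 reminders may run weekly for six weeks, to about two and a half months after randomization and so close to the 3-month wave. The discontinuation reason in 7.2 is permissive. Section 9.4.1 already concedes that missing at random may fail and plans imputation and sensitivity analyses.

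Much of this stands, and it rules out three stronger inferences that a reader might draw:

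- **That one unreturned form alone means withdrawal.** It does not; a relative who can be reached is not withdrawn.
- **That the loss falls on the most distressed or newly bereaved relatives.** The documents give no evidence on who becomes unreachable. For deaths, 2.3.1, 4.1 and 5.5 delay materials by about a month, and 4.1 puts an after-death form in place of the next questionnaire. Its worked example still sends the 6-month form.
- **That power is endangered.** Step 2 does not show that.

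The reply does not remove the ambiguity. The action list is worded as obligatory, starts from one form and does not wait for later waves, and no section says that someone recorded as withdrawn still receives questionnaires.

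**Conclusion.** The point holds as an ambiguity with an avoidable cost. Section 7.3 supports both a one-wave and an all-waves reading, and the one-wave reading conflicts with the contact schedule. Loss of month-3 or month-6 HADS-D scores is possible on that reading; it is not established.

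The size is modest. At ICC 0.2 and 10–30% unreachable per wave, the detectable difference would be 0.91–1.11 points instead of 0.86–0.94. The highest value examined, 1.22 at ICC 0.4 and 30%, is still below the lower stated MCID of 1.6. These figures rest on assumed, independent misses and one relative per patient. The main harms are scores needlessly forgone, heavier reliance on the missing-at-random assumption, and inconsistent handling between staff. The change is worth making because it is cheap and brings conduct into line with the primary model.

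**What to change.** Amend 7.3 to say three things:

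1. Non-response or failed contact at one wave is a missed assessment for that wave only.
2. The 3- and 6-month questionnaires are still sent to every participant who has not asked to stop.
3. Lost-to-follow-up status is assigned only once the 6-month attempts are exhausted.

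The lost-to-follow-up reason in 7.2 should then be read by that definition; it need not be deleted. The cost is a wording amendment and a few extra mailings or calls. No sample-size figure and no part of the primary model changes.
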